## 5 STUDY PRODUCT

Subjects will have access to Akynzeo® as per their usual means for obtaining prescription medications utilizing a study drug access card.

### 5.1 Dosage and Administration

Following the screening period patients meeting the inclusion/exclusion criteria will receive their dose of Akynzeo® on the day of their chemotherapy administration for each cycle. Each patient will be treated with the recommended dose of Akynzeo® for highly emetogenic chemotherapy, including cisplatin based chemotherapy, as per the Canadian Product Monograph. The recommended dose of Akynzeo® is 1 capsule of Akynzeo® administered orally approximately 1 hour prior to the start of each chemotherapy cycle with dexamethasone 12 mg to be administered orally 30 minutes prior to chemotherapy. Day 2-4 dexamethasone 8 mg orally once daily.

For anthracycline and cyclophosphamide based chemotherapy the recommended dose of Akynzeo is 1 capsule of Akynzeo® administered orally approximately 1 hour prior to the start of each chemotherapy cycle with dexamethasone 12 mg to be administered orally 30 minutes prior to chemotherapy. Administration of dexamethasone on days 2-4 is not necessary.

### 5.2 Concomitant Medication(s)

Other treatment considered necessary for the subject's welfare may be given at the discretion of the patients treating physician. All such therapy must be recorded in the Case Report Form.

## 6 STUDY PROCEDURES

The Time and Event Schedule which is found at the end of the protocol synopsis summarizes the type (efficacy, safety, etc.) and frequency of each study procedure to be performed in this study.

No study specific procedure will be performed prior to obtaining written consent of the study subject.

### 6.1 Visit 1 / Screening (28 to 0 days prior to visit 2)

The following will be performed at visit 1:

- Signed and dated Informed Consent Form
- Medical history (including oncologic history)
- Demographics
- Eligibility assessment
- Nausea Assessment previous or ongoing
- Pregnancy testing in females of childbearing potential will be performed as per the investigators/institutions standard practice for chemotherapy patients
- Assessment of current medications (antiemetic's, anti-tumor drugs, other concomitant medications)
- Patient kit distribution and education on contents (Can also be distributed at Visit 2)

### 6.2 Visit 2 (1st Day of cycle 1)

- Akynzeo® taken by patient one hour prior to chemotherapy administration
- Diary completed days 1-5 (0-120 hours post chemotherapy administration)
  - Day 1 is defined as a 24-hour period starting at the time chemotherapy is administered (0-24 hours)
  - Day 2 is defined as 25-48 hours after start of chemotherapy
  - Day 3 is defined as 49-72 hours after start of chemotherapy
  - Day 4 is defined as 73-96 hours after start of chemotherapy
  - Day 5 is defined as 97-120 hours after start of chemotherapy
- FLIE is completed after the end of Day 5/120 hours after start of chemotherapy administration
- WPAI-NV completion is completed after the end of Day 5/120 hours after start of chemotherapy administration
- Assessment of adverse events
- Assessment of concomitant medications

### 6.3 Visit 3 (1st Day of cycle 2)

- Akynzeo® administered, Diary, FLIE and WPAI-NV collection and review
- Distribute diary, FLIE and WPAI-NV for cycle 2
- Assessment of adverse events
- Assessment of concomitant medications
- Note: Patient will complete their daily diary from Day 1 to Day 5

### 6.4 Visit 4 (1st Day of cycle 3)

- Akynzeo® administered, Diary, FLIE and WPAI-NV collection, review
- Distribute diary, FLIE and WPAI-NV for cycle 3
- Assessment of adverse events
- Assessment of concomitant medications
- Note: Patient will complete their daily diary from Day 1 to Day 5

### 6.5 Visit 5 (1st Day of cycle 4)

- Akynzeo® administered, Diary, FLIE and WPAI-NV collection and review Distribute diary, FLIE and WPAI-NV for cycle 4
- Assessment of adverse events
- Assessment of concomitant medications
- Note: Patient will complete their daily diary from Day 1 to Day 5

### 6.6 Visit 6 / Final Visit (should occur prior to start of next chemotherapy cycle)

- Collect completed diary cards, FLIE and WPAI-NV
- Assessment of adverse events
- Assessment of concomitant medications
- Complete study completion/early termination form

### 6.7 Effectiveness Assessments

The response to Akynzeo® and the necessity for use of a rescue medication will be recorded to evaluate effectiveness. Any medicinal products used as rescue medication will also be recorded in the patient diary.

The following parameters will be recorded in the patient diary:

- Severity of nausea (daily from Day 1 to Day 5) using a VAS (Visual Analogue Scale)

- Time to failure (time to first emetic episode or time to rescue)
- Use of rescue medication (daily from Day 1 to Day 5)

Note: A Complete Response (CR) is defined as no emetic episode and no use of rescue medication during the observational period (Day 1 to Day 5).

## 6.8 Patient Assessments

### 6.8.1 Functional Living Index - Emesis (FLIE)

The quality of life of patients will be collected by means of the FLIE questionnaire on administration of Akynzeo® during chemotherapy.

The Functional Living Index – Emesis (FLIE) questionnaire is a patient reported outcome (PRO) validated tool with the objective of assessing the impact of chemotherapy-induced nausea and vomiting on patient's daily function.

It consists of a nausea domain and a vomiting domain of nine items each where the patient should rate how much nausea and vomiting have affected the quality of life. For each question the patient will rate how much nausea (or vomiting) has affected an aspect of his quality of life during the past five days. Each question uses a visual analogue scale (VAS).

The investigator shall be responsible for explaining to the patient how the questionnaire should be correctly completed.

The FLIE will be completed by the patient on Day 5 of chemotherapy cycles 1, 2, 3 and 4.

### 6.8.2 Patient Diary

The patient diary will be completed daily for the first five days of each cycle (starting on the day chemotherapy is administered). The patient diary will report daily occurrence and intensity of nausea (utilizing a VAS) and vomiting, rescue medications, adverse events (excluding nausea and vomiting), concomitant medication use for CINV.

The patient diary will be included in the Patient Kit will be distributed at Visit 1 and collected at Visits 3 through 6.

### 6.8.3 WPAI-NV (Work Productivity Activity Impairment – Nausea and Vomiting)

The WPAI-NV is a 7-item questionnaire that assesses the effect of nausea and vomiting on a patient's ability to work and perform regular activities.

The WPAI-NV will be completed by the patient after Day 5 of chemotherapy cycles 1, 2, 3 and 4.

### 6.8.4 Health Economics Outcome Research (HEOR) Assessments

The following outcomes of health resource utilisation will be collected:

- Hospitalisations
- The number of ER visits

Health resource utilisation will be recorded on the patient diary and collected for all patients participating in the study.

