EXCLUSION CRITERIA (as per Contraindications in the approved Canadian Product Monograph)	
 
• Women of child bearing potential who are pregnant, planning on becoming pregnant or breast feeding.
 
• Hypersensitivity to active substances, excipients or other ingredients of Akynzeo®.
 
• Concomitant use of pimozone, terfenadine, astemizole, or cisapride.
 
• Patient is enrolled in another clinical trial where antiemetic treatment is pre-specified by the study protocol.
 

---

STUDY DURATION	This study will last approximately 20 months from 1 st patient enrolled until last patient has completed. The observation period for each subject will last 4-6 months.
RECRUITMENT PERIOD	Approximately 12 months
ANALYSIS	Descriptive statistics will be generated for the primary, secondary and exploratory endpoints.

Table 1: Time and event schedule

Activity	Screening/ Visit 1	Visit 2 Cycle 1	Visit 3 Cycle 2	Visit 4 Cycle 3	Visit 5 Cycle 4	Visit 6/Final visit
Time period	-28 days to Day 1, Cycle 1	Day 1 of Cycle 1	Day 1 of Cycle 2	Day 1 of Cycle 3	Day 1 of Cycle 4	Within 28 days of Cycle 4 or prior to start of next chemotherapy cycle
Informed consent	X					
Inclusion/Exclusion	X					
Demographics & Medical History	X					
Nausea assessment - physician	X					
Current treatments/medications	X					
Patient Kit (distribute and provide education on use)	X*					
Patient Assessments:						
Patient diary, including: 
 
• Nausea Severity Assessment
 
• Rescue medications
 
• Adverse Events
 
		X 	X 	X 	X 	
• Functional Living Index – Emesis (FLIE)		X 	X 	X 	X 	
• Work Productivity Activity Impairment Scale – Nausea and Vomiting (WPAI-NV)		X 	X 	X 	X 	
Patient Kit - collect and review diary and questionnaires			X	X	X	X
Concomitant medication		X	X	X	X	X
Adverse event		X	X	X	X	X
Study completion assessment/early discontinuation						X

\*Patient Kit can be distributed at Screening/Visit 1 or Visit 2. All assessments/training should be completed prior to chemotherapy treatment

 Patient completes diary on days 1-5 (0-120 hours) post chemotherapy cycle

 Patient completes FLIE and WPAI after day 5 of cycle

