## 2.3 Exploratory Outcomes

Health economic and outcomes research data will be collected and recoded on the diary card specifically emergency department (ED) visits and hospitalizations.

Work Productivity Activity Impairment scale for Nausea and Vomiting (WPAI-NV) will be collected on day 5 of each cycle.

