### 7.3 Efficacy and Safety Analysis

This is a two year (approximately), multi-centre, prospective, observational study designed to collect clinical data on the real-world use of Akynzeo® in Canada. All analyses will be descriptive in nature.

Before beginning data analysis, plausibility checks will be performed. Implausible or ambiguous data will be excluded from analysis.

Prior to database lock, a statistical analysis plan (SAP) defining all details of analysis will be prepared. A table mock-up (TMU) document which will illustrate the details of presentation and analysis for data collected in this study will accompany this document.

The Intent-To-Treat (ITT) population includes all patients who were entered into the study web-based application and have a date of signed informed consent available. This population will be used to provide descriptives for patients enrolled by centre, patient disposition and reasons for screen failure.

The modified Intent-To-Treat (mITT) population includes all patients who were included in the ITT population and fulfilled all entry criteria and received at least one dose of the study treatment (Akynzeo®). Missing questionnaires/assessments will not be imputed. The mITT population will be used for the analysis of the primary, secondary and exploratory endpoints not including health resource utilisation (ER visits, hospitalizations). This population will also be used for demographic, medical history and concomitant medication tables.

The Safety population includes all patients who received at least one dose of the study treatment (Akynzeo®). This population will be used for all safety analyses and health resource utilisation (ER visits, hospitalizations) tables.

Continuous variables will be summarized descriptively by number of observations, number of missing observations, mean, standard deviation, median, 1st quartile, 3rd quartile, minimum and maximum. Categorical variables will be summarized descriptively as frequency counts and percentages.

A number of p-values may be presented in the reported tables for exploratory purposes. Statistical testing will be performed at the two-sided 0.05 significance level unless otherwise specified. P-values will not be adjusted for multiple comparisons.

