### 8.1 Adverse Event Definitions

According to the currently valid Directive of the European Parliament and of the Council relating to the implementation of good clinical practice in the conduct of clinical studies on medicinal products for human use (2001/20/EC), an adverse event (AE) is “Any untoward medical occurrence in a patient or clinical study subject administered a medicinal product and which does not necessarily have a causal relationship with this treatment”. An AE could therefore be any unfavourable or unintended sign (for example, an abnormal laboratory finding), symptom or any disorder with a temporal relationship to the use of a medicinal product, regardless of whether or not it is considered to be related to use of the medicinal product.

In the context of this study, all adverse events (AEs) from the time of Akynzeo® administration over a period of 5 days during the chemotherapy cycles which are part of the observation period will be documented on the appropriate pages of the eCRF.

A serious adverse event (SAE) is defined as an AE that:

- results in death;
- is life-threatening;
- requires hospitalization or prolongation of existing hospitalization;
- results in persistent or significant disability or incapacity;

---

 This includes every AE that – in the opinion of the investigator – is life-threatening for the study subject. This definition does not include events that may have led to death, if they had occurred in a more severe form.

- is a congenital anomaly or results in a birth defect or
- significant medical events that may endanger patients or require an intervention to prevent the above characteristics or consequences.

An unexpected adverse event is any event for which, with regard to its nature, severity or incidence, no details have been included to date in the current Product Monograph for Akynzeo®. The assessment of the "expectedness" of an AE is performed by the sponsor.

Planned surgical interventions or hospitalizations scheduled before the informed consent form was signed but carried out during the study period (study procedures, chemotherapy cycles, etc.) are not to be regarded as (serious) AEs.

The investigator assesses whether or not an event qualifies as a serious adverse event (SAE, see criteria above).

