**EMERGENCY DEPARTMENT VISITS OR OVERNIGHT HOSPITALIZATION**

1. Did you visit an Emergency Department during the 120 hours (5 days) after the start of chemotherapy?  
 No    Yes → If you visited the Emergency Department, please check the applicable box(es) or provide the reason, and record the date, onset time and end time of each visit.

Nausea	Vomiting	Other Reason	Date	Onset Time 00:00 – 23:59	End Time 00:00 – 23:59																								
			
 
 										
 
 dd	mmm	yyyy	hh	mm	hh	mm	
 
											dd	mmm	yyyy	hh	mm	hh	mm	
 
 				
 
 hh	mm	hh	mm	
 
					hh	mm	hh	mm
dd	mmm	yyyy	hh	mm	hh	mm																							
hh	mm	hh	mm																										

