			
 
 										
 
 dd	mmm	yyyy	hh	mm	hh	mm	
 
											dd	mmm	yyyy	hh	mm	hh	mm	
 
 				
 
 hh	mm	hh	mm	
 
					hh	mm	hh	mm
dd	mmm	yyyy	hh	mm	hh	mm																							
hh	mm	hh	mm																										

2. Were you hospitalized overnight during the 120 hours (5 days) after the start of chemotherapy?  
 No    Yes → If you were hospitalized overnight, please check the applicable box(es) or provide the reason, and record the date, onset time and end time of each overnight hospitalization.

Nausea	Vomiting	Other Reason	Date	Onset Time 00:00 – 23:59	End Time 00:00 – 23:59																								

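### ED visits and hospitalisations are taken from the patient diary alone, so an admission already held as an SAE can be missing from the resource-use table

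*Combined protocol and SAP*

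**What the plan says.** Section 2.3 names the diary as the source: "Health economic and outcomes research data will be collected and recoded on the diary card specifically emergency department (ED) visits and hospitalizations". Section 6.8.4 repeats this: "Health resource utilisation will be recorded on the patient diary and collected for all patients participating in the study". The visit procedures in sections 6.1 to 6.6 contain no staff question about ED visits or admissions.

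The diary page in Appendix 2 asks two questions for each cycle: "Did you visit an Emergency Department during the 120 hours (5 days) after the start of chemotherapy" and "Were you hospitalized overnight during the 120 hours (5 days) after the start of chemotherapy". The booklet comes back at the next visit.

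Sites also hold a second record. Under section 8.1 an adverse event is serious if it "requires hospitalization or prolongation of existing hospitalization". Section 8.3 has the site send every SAE, related or not, within 24 hours of detecting it.

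For the analysis, section 7.3 assigns resource use to the Safety population, meaning everyone who took at least one dose: "This population will be used for all safety analyses and health resource utilisation (ER visits, hospitalizations) tables". It gives no rule for a dosed patient without a diary in these tables and describes no reconciliation with SAE records.

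**The concern.** The resource-use table covers all dosed patients, but its only input is a form that the patient must complete and bring back. A patient admitted late in the five-day window may be in hospital when the diary falls due, and one who stops treatment after an admission may not return it. If the site knows of the admission, it holds it as an SAE. The report can then list that SAE while the resource-use table shows the same patient as missing or, depending on how the table is programmed, as not admitted.

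Two things are at stake. ED visits and hospitalisations are the only two resource-use outcomes, and section 1.2 presents real-world data as informative on resource use and cost, so under-capture would make the rates look more favourable than they are. A reader who compares the safety and resource-use tables may also find admissions that do not match.

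**Working it through.** The plan states no expected ED or admission rate, no diary return rate and no sample size calculation, so there is no figure to reproduce. The check has two parts.

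**1. What each source can hold within 0-120 h of a cycle**

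| Event | Diary (if returned) | AE/SAE record |
|---|---|---|
| Unplanned overnight admission for an AE | Yes | Yes, as an SAE (8.1) |
| Admission for nausea or vomiting | Yes, with a tick box for the reason | Uncertain: the Synopsis keeps nausea and vomiting out of the safety records |
| Admission scheduled before consent | Yes, if overnight | No (8.1) |
| ED visit without admission | Yes | Not an SAE on that ground alone |

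Neither source contains the other. Only the diary asks about ED visits; the SAE route can hold an admission when no diary comes back. The comparison must stay within 0-120 h. The diary covers 4 cycles × 5 days = 20 days, whereas the Synopsis states: "The observation period for each subject will last 4-6 months". Later SAE admissions are outside what the diary asks, so their absence from the resource-use table is not an inconsistency.

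**2. How large the understatement could be**

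Let h be the true proportion of cycles with an admission, a the diary return in those cycles and b the return in other cycles.

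- Returned diaries only: observed rate = h·a / [h·a + (1 − h)·b]; relative shortfall = 1 − a / [h·a + (1 − h)·b].
- Missing diary read as no event: observed rate = h·a; relative shortfall = 1 − a.

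All values of h, a and b below are assumptions; only the 200 patients and four cycles come from the protocol.

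*Base case.* 200 × 4 = 800 patient-cycles, h = 3% (24 admissions), a = 0.70, b = 0.95.

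- Admissions seen: 24 × 0.70 = 16.8.
- Diaries returned: 16.8 + 776 × 0.95 = 754.
- Returned diaries only: 16.8 / 754 = 2.23%, which is 26% below 3%.
- Missing as none: 16.8 / 800 = 2.10%, which is 30% below 3%.

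*Range.* h = 2-5%, non-return 20-40% in cycles with an admission and 5-10% in others.

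| h | a | b | Shortfall, returned diaries | Shortfall, missing as none |
|---|---|---|---|---|
| 2% | 0.80 | 0.90 | 1 − 0.80/0.898 = 10.9% | 20% |
| 5% | 0.80 | 0.90 | 1 − 0.80/0.895 = 10.6% | 20% |
| 2% | 0.60 | 0.95 | 1 − 0.60/0.943 = 36.4% | 40% |
| 5% | 0.60 | 0.95 | 1 − 0.60/0.9325 = 35.7% | 40% |

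The span is about 11% to 40%. The 40% end requires missing to be counted as none; among returned diaries the maximum is about 36%.

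*Equal return.* With a = b the first formula reduces to h, so there is no bias among returned diaries. For example, with h = 10% and a = b = 0.90: 0.09 / (0.09 + 0.81) = 10.0%. Counting missing as none would still give 9.0%.

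**The case against.** A reader might infer that admitted patients do return fewer diaries, and hence that the rates are biased downward. The documents do not support that as a fact. They give no return rates, and two procedures work against it: study personnel collect the diary at the next visit and review it with the patient (Table 1, Appendix 2), and a patient who leaves early should undergo the final-visit assessments, which include diary collection (4.4, 6.6). A discharged patient can still answer two yes/no questions at that review. These safeguards stand, but only for patients who attend; they do not help for one who dies or is lost to follow-up.

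A reader might also infer that the plan treats a missing diary as no admission. It does not say so. The no-imputation sentence in section 7.3 sits in the mITT paragraph, which excludes resource use, and declining to impute is not the same as recording no event. What stands is that no rule is given.

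Nor is the SAE record a complete reference. It misses ED visits, pre-scheduled admissions and possibly CINV admissions, which matter most here. It also depends partly on the patient: section 6.9 has adverse events reported by the subject or, when appropriate, a caregiver or representative, and the 24 hours in section 8.3 run from detection. Some patients may be missed by both routes. Adding SAE records alone could shift the recorded reasons towards non-CINV admissions.

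Finally, section 7.3 leaves the details to a SAP to be prepared before database lock, which is not part of the text reviewed and could contain a reconciliation. The endpoint is also exploratory and descriptive (3.6, 7.3).

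**Conclusion.** The point holds as a gap in sources and derivation, not as a demonstrated bias. The protocol takes ED visits and hospitalisations from the diary alone, tabulates them on all dosed patients, and neither uses nor reconciles the admissions that sites hold as SAEs. Where a diary is missing or incomplete, resource use may be understated and the two tables may disagree.

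The amount is unknown. It can be zero among returned diaries, or about 11-40% under the differential non-return assumed above. The possible disagreement between tables does not rest on those assumptions: one known SAE admission in the window without a completed diary page is enough.

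The primary FLIE analysis is unaffected. This is a minor, inexpensive improvement.

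**What to change.** In sections 6.8.4 and 7.3, and in the SAP:

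- Count a hospitalisation or ED visit if it is recorded in the diary **or** on an AE, SAE or Special Situation form with a start date inside the cycle's 0-120 h window. Special Situation forms belong in the list because lack of efficacy is reported on them (8.1, 10) and they may hold CINV admissions.
- Add one prompt to the existing review at Visits 3 to 6: any ED visit or admission in the 120 h after the last chemotherapy, with date and reason. SAE records alone cannot supply ED visits, pre-scheduled admissions or, possibly, CINV admissions.
- Reconcile the Synopsis, which excludes nausea and vomiting from the safety records, with the hospitalisation criterion in section 8.1, so that it is clear whether a CINV admission is recorded as an SAE.
- Use as denominator the dosed patient-cycles with a returned diary or an answered prompt. Show the number of cycles with neither; do not count them as event-free.
- Report by reason and by source (diary only, safety form or prompt only, both).

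The cost is one prompt at an existing visit and a short derivation. Visits, treatment and patient questionnaires do not change. The reported rates may come out slightly less favourable.
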